5.6 Changes to Planned Analyses

Any changes to the planned statistical analyses made prior to performing the analyses will be documented in a Statistical Analysis Plan approved prior to performing the analyses.

6 VALIDATION

All clinical data reports generated per this plan will be validated per Global WI: Clinical Data Reporting Validation.

7 PROGRAMMING CONSIDERATIONS

7.1 Statistical Software

All statistical analyses will be done using The SAS System software, version 8 or higher (Copyright © 2000 SAS Institute Inc., [name], USA. All rights reserved). Other statistical software (e.g. StatXact) may be used if necessary.

7.2 Format of output

Results of analysis will be output programmatically to Word documents from SAS with no manual intervention. All output for the final statistical report will be in the form of a Word document containing tables, figures, graphs, and listings, as appropriate.

7.3 Rules and Definitions

Binary event rates (proportions) will be reported on a per patient basis.

The last follow-up date will be the latest of the following dates for each patient: date of an adverse event, index procedure date, follow-up visit date, any stent or ECRP procedure date, stent removal date, and device event date.

Stricture resolution at 24 months is defined by the following two criteria being met:

• Absence of re-stenting after the per-protocol stenting period through the 24 month visit

Version AA March 20, 2013 Boston Scientific WallFlex Biliary FC CP RCT SAP 90913894/Ver. AA Page 12 of 13 • Absence of cholestasis at the 24 month visit, defined as alkaline phosphatase level not exceeding 2 times the level at completion of the per-protocol stenting period

Primary endpoint failures are 1) subjects who are re-stented during follow-up after the per-protocol stenting period and 2) subjects who have not been re-stented at month 24 but have alkaline phosphatase level exceeding 2 times the level at completion of the per-protocol stenting period.

Subjects who experience early stent removal or complete distal stent migration without subsequent re-stenting will not be considered failures. If re-stenting occurs, but the cumulative stenting period does not exceed 12 months, the subject remains eligible for primary endpoint assessment.

For the final tables, two-sided exact tests will be done to test for differences between the two groups for removability and AEs. A one-sided non-inferiority Farrington-Manning test will be done to see if stricture resolution is non-inferior in the Metal group compared to the Plastic group. A two-sided student's t-test will done to test for differences between the two groups for the number of ERCP procedures done.

Version AA March 20, 2013 Boston Scientific WallFlex Biliary FC CP RCT SAP 90913894/Ver. AA Page 13 of 13

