4.2. Secondary Endpoints

1. Occurrence of adverse events related to the stent and/or the stent placement or removal procedures
2. Number of ERCP procedures through 24 months after initial stent placement
3. Ability to deploy the stent(s) in satisfactory position
4. Stent Removal:
 - Ability to remove the stent(s) without serious stent removal related adverse events at each procedure involving removal of stent(s) (technical success at removal) or
 - Complete distal migration without serious stent removal related adverse events
5. Liver Function Tests (LFT's)
 - Baseline LFTs compared to LFTs taken at time of original plastic stent placement for any subject with a prior plastic stent
 - LFT improvement at 1 month post-study treatment compared to baseline LFTs (and/or compared to LFTs taken at time of original plastic stent placement for any subject with a prior plastic stent)
 - LFTs at month 24 compared to LFTs at removal of last stent (applicable for subjects who had not been re-stented at time of month 24 visit)
6. Health Economic Endpoints:
 - Number of outpatient procedures
 - Number of hospitalizations
 - Duration of hospitalizations

- Length of procedures
- Number of devices

5. Design

The study is designed as a post-market, multi-center, prospective, non-blinded, randomized study. At least 164 subjects (82 per arm) will be treated with 1:1 randomization between Group A and Group B and will be followed through 24 months post-initial stent(s) placement:

- Subjects in the MS arm will be treated with a single metal stent, which will be removed 12 months post-placement.
- Subjects in the PS arm will receive 2 plastic stents when possible. Subjects in this arm will undergo plastic stents exchange/bile duct calibration at 4 and 8 month post-initial stent placement. At each stent exchange, the goal should be to provide progressive stent therapy by increasing the number of plastic stents at 4 months and again at 8 months. Final plastic stent removal will occur 12 months post-initial stent placement.

5.1. Inclusion Criteria:

- Age 18 or older
- Willing and able to comply with the study procedures and provide written informed consent to participate in the study
- Chronic pancreatitis

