5 ADDITIONAL DATA ANALYSES

5.1 Secondary Endpoints

- 1. Occurrence of adverse events related to the stent and/or the stent placement or removal procedures
- 2. Number of ERCP procedures through 24 months after initial stent placement
- 3. Ability to deploy the stent(s) in satisfactory position
- 4. Stent Removal:

Version AA March 20, 2013 Boston Scientific WallFlex Biliary FC CP RCT SAP 90913894/Ver. AA Page 10 of 13

- a. Ability to remove the stent(s) without serious stent removal related adverse events at each procedure involving removal of stent(s) (technical success at removal) or
- b. Complete distal migration without serious stent removal related adverse events
- 5. Liver Function Tests (LFT's)
 - a. LFT improvement at month 1 compared to baseline naïve stricture or to LFTs at time of plastic stent placement 6 months or fewer prior to enrollment in strictures treated with 1 prior plastic stent.
 - b. LFTs at month 24 compared to removal of last stent (applicable for subjects who had not been re-stented at time of month 24 visit)
- 6. Health Economic Endpoints:
 - Number of outpatient procedures
 - Number of hospitalizations
 - o Duration of hospitalizations
 - Length of procedures

The secondary endpoints will be summarized using descriptive statistics (mean, standard deviation, n, minimum, maximum) for continuous variables and frequency statistics for discrete variables. Statistical testing will be performed using appropriate methods. For analysis of LFT's, McNemar's Test or repeated measures regression model may be used.

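### Removal success is defined per removal procedure but tested per patient, so the test compares cumulative removal risk (three scheduled plastic removals against one metal) and not technical success of a removal

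*SAP*

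**What the plan says.** The removal endpoint in SAP 5.1 (same wording in Protocol 4.2) has two routes to success. One is "Ability to remove the stent(s) without serious stent removal related adverse events at each procedure involving removal of stent(s", which the documents label technical success at removal. The other is "Complete distal migration without serious stent removal related adverse events".

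SAP 7.3 sets the unit of reporting, "Binary event rates (proportions) will be reported on a per patient basis", and the test: "two-sided exact tests will be done to test for differences between the two groups for removability and AEs".

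The schedules are in Protocol section 5 (Design). For metal: "Subjects in the MS arm will be treated with a single metal stent, which will be removed 12 months post-placement". For plastic: "Subjects in this arm will undergo plastic stents exchange/bile duct calibration at 4 and 8 month post-initial stent placement", and then "Final plastic stent removal will occur 12 months post-initial stent placement". That is one scheduled removal for metal and three for plastic, since an exchange involves taking stents out.

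The plan gives no rule for combining several removals into one patient result, no per-removal rate, no clustered model for removal and no restriction to the final removal. SAP 5.1 names a repeated-measures model for liver function tests only. SAP 5.5 adds exploratory predictor models for removability.

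**The concern.** The endpoint and its test use different units. The definition asks whether a given removal went well. The test asks whether a patient got through all of that patient's removals, and the number of removals differs between arms because of the treatment schedule.

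Two misreadings follow. If the two stent types are equally safe to remove, plastic will still show lower per-patient success, and a reader of a result called removability would credit metal with being easier to remove. Conversely, if metal is harder to remove, the threefold difference in scheduled removals can cancel that out. For a study of removable metal stents, the second case matters at least as much as the first.

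**Working it through.** **Inputs from the documents.** Scheduled removals are m = 1 (metal, month 12) and m = 3 (plastic, months 4, 8 and 12), from Protocol section 5. There are 82 per arm (SAP 3.1.2: 74 × 1.10 = 81.4, rounded up). The test is two-sided exact (SAP 7.3).

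**Assumptions, because the documents are silent.** The per-removal failure probability p is set at 1%, 2%, 5% or 10%, equal in both arms. Alpha is 0.05. The exact test is taken to be Fisher's. A patient succeeds only if every removal succeeds. Failures are independent within a patient, and every patient is evaluable. The plan states no expected rate or power for removal, so there is no figure of its own to reproduce.

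**Formula.** Per-patient success = (1 − p)^m. For p = 5%, metal is 0.95 and plastic is 0.95³ = 0.857. The rejection probability comes from full enumeration of both binomial distributions.

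| p per removal | Metal success (1 removal) | Plastic success (3) | Test rejects | Plastic success (2) | Test rejects |
|---|---|---|---|---|---|
| 1% | 99.0% | 97.0% | 1.7% | 98.0% | 0.3% |
| 2% | 98.0% | 94.1% | 10.9% | 96.0% | 2.6% |
| 5% | 95.0% | 85.7% | 43.9% | 90.3% | 13.5% |
| 10% | 90.0% | 72.9% | 76.2% | 81.0% | 29.9% |

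The two-removal columns matter because Protocol 7.4.5 allows for plastic patients who are not re-stented after month 4 or 8. Nearly all rejections favour metal. With one removal in each arm and equal p, the same test rejects in at most 2.9% of trials over this range (1.7% at p = 5%).

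**Within-patient correlation.** A beta-binomial model with three plastic removals and p = 5% gives plastic success of 87.0%, 89.2% and 91.1% at correlations 0.1, 0.3 and 0.5. The test then rejects in 34%, 19% and 10% of trials. At p = 2% and correlation 0.3 it rejects in 4.0%. With two removals, p = 5% and correlation 0.3, it rejects in 7.5%. The gap closes fully only at correlation 1.

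**Masking.** Suppose metal fails in 6% of removals and plastic in 2%. Per patient, metal fails in 6.0% and plastic in 1 − 0.98³ = 1 − 0.9412 = 5.9%. A threefold difference per removal disappears.

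**The case against.** **A per-patient comparison is legitimate.** Patients are randomised to strategies, and needing more removals is a consequence of the assigned strategy. A reader might infer that a significant result under equal per-removal risk is a false positive, built into the plan in favour of the sponsor's device. The documents do not support that. The objective in Protocol section 3 covers complications and number of procedures over 24 months. If plastic patients truly face a 14.3% cumulative risk and metal patients 5%, rejecting equality per patient is correct. The fault lies in what the result would be called.

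**The all-removals rule is inferred.** SAP 7.3 does not state it, and its sentence on exact tests names no unit. The study event schedule (Protocol Table 1) lists stent removal only at months 11–12 and puts months 4 and 8 under placement/exchange, so a reading with one removal per patient is not excluded. It is the weaker reading, because an exchange involves removal. The silence still leaves the choice open in an unblinded trial.

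**The size is uncertain.** No failure rate is given, and complete distal migration without a serious removal-related event counts as success. Independence with exactly three removals is an upper-end case. A reader might take 44% or 76% as likely; nothing in the documents shows that those failure rates are realistic.

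**The per-removal analysis has weaknesses.** The number of removals is determined after randomisation, and a clustered logistic model can be unstable with few failures. Both points stand. They are reasons to keep the exact test beside the new analysis, not to leave the analysis out.

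**This is one secondary endpoint.** The sample size and the non-inferiority decision rest on stricture resolution. That stands and limits the weight of the point.

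**Conclusion.** The definition and the test do not match, and the plan does not reconcile them. On the natural reading, the exact test measures cumulative per-patient removal risk under each strategy. It cannot support a statement about technical success of a removal in either direction.

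The size depends on an assumed failure rate. At 1–2% per removal, the distortion is mainly in the estimate (2 to 4 percentage points with three plastic removals), and the test rejects in 1.7% to 10.9% of trials. At 5% it is material: 9.3 points and 43.9% with three independent removals, falling to 13.5% with two and lower again with within-patient correlation. The direction needs only that plastic patients have more removals on average and that failures within a patient are not perfectly correlated.

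The primary analysis is unaffected. This is an inexpensive improvement that lets the trial answer the question its own endpoint names.

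**What to change.** Amend SAP 7.3 as follows.

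1. State how several removals become one patient result, for example success only if every removal succeeds, and how complete distal migration and patients with no removal are counted.
2. Keep the per-patient exact test, but label it cumulative removal risk by strategy.
3. Add a per-removal comparison clustered by patient: logistic GEE, or a cluster-bootstrap confidence interval for the risk difference. Base any statement about technical success at removal on this analysis.
4. Report the number of removals per patient in each arm beside both results.
5. If failures are too few for the clustered analysis, use an exact test on the final (month 12) removal, and set the threshold for that switch in advance.

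The cost is SAP wording and one extra secondary analysis. It needs removal outcomes recorded by procedure. The endpoint definition implies this, but the case report form is not in the documents, so it should be confirmed. The added analysis may be unstable with few failures, and it is affected by the post-randomisation number of removals. It should be read beside the per-patient result, not in place of it.

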The Investigator will maintain, at the investigative site, in original format all essential study documents and source documentation that support the data collected on the study subjects in compliance with ICH/GCP guidelines. Documents must be retained for at least 2 years after the last approval of a marketing application or until at least 2 years have elapsed since the formal discontinuation of the clinical investigation of the product. These documents will be retained for a longer period of time by agreement with BSC or in compliance with other local regulations. It is BSC's responsibility to inform the Investigator when these documents no longer need to be maintained. The Investigator will take measures to ensure that these essential documents are not accidentally damaged or destroyed. If for any reason the Investigator withdraws responsibility for maintaining these essential documents, custody must be transferred to an individual who will assume responsibility, and BSC must receive written notification of this custodial change.

10. Potential Risks and Benefits

10.1. *Anticipated Adverse Device Effects*

As per the commercial DFU included with the study devices, the potential complications associated with metal stent placement include, but are not limited to:

- Pain
- Bleeding
- Fever
- Nausea
- Vomiting
- Infection
- Inflammation
- Stent occlusion
- Tumor overgrowth around ends of stent
- Tumor ingrowth through the stent
- Mucosal hyperplasia
- Cholangitis
- Cholecystitis*
- Pancreatitis
- Ulceration of duodenum or bile duct
- Perforation of duodenum or bile duct
- Stent migration
- Death (other than that due to normal disease progression)
- Stent misplacement
- Perforation of the gallbladder due to the stent covering the cystic duct*
- Stent Fracture
- Hepatic abscess

*Note: In a small clinical trial of this device, two out of four (50%) subjects who had a stent placed across the cystic duct developed cholecystitis. One of these subjects suffered a perforated gallbladder due to the stent covering the cystic duct, requiring a drain to be placed.

As per the commercial DFU included with the study devices, potential complications associated with stent removal include, but are not limited to:

- Pain
- Bleeding
- Fever
- Nausea
- Vomiting
- Infection
- Inflammation
- Recurrent obstructive jaundice
- Mucosal hyperplasia
- Cholangitis
- Cholecystitis
- Pancreatitis
- Ulceration of duodenum or bile duct
- Perforation of duodenum or bile duct

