Serious Adverse Device Effect (SADE) Ref: ISO 14155-2011	An adverse device effect that has resulted in any of the consequences characteristic of a serious adverse event. 
Note: All SAEs that could have led to a SADE if suitable action had not been taken or if circumstances had been less fortunate shall be reported as required by the local IRB/EC, national regulations, or the protocol. If applicable, see MEDDEV 2.7/3 12/2010 for reporting timeline requirements.

Device Deficiency Ref: ISO 14155-2011 Ref: MEDDEV 2.7/3 12/2010	A device deficiency is any inadequacy of a medical device with respect to its identity, quality, durability, reliability, safety or performance. 
Note: Device deficiencies include malfunctions, use errors, and inadequate labeling.
 
Note: All device deficiencies that could have led to a SADE if suitable action had not been taken or if circumstances had been less fortunate shall be reported as required by the local IRB/EC, national regulations, or the

Table 11.1-1: Adverse Event Definitions

Term	Definition
	protocol. If applicable, see MEDDEV 2.7/3 12/2010 for reporting timeline requirements.

Abbreviations: EC=Ethics Committee; IRB=Institutional Review Board

Underlying diseases are not reported as AEs unless there is an increase in severity or frequency during the course of the investigation. Death should not be recorded as an AE, but should only be reflected as an outcome of a specific SAE (see Table 11.1-1 for AE definitions).

Any AE experienced by the study subject after informed consent, whether during or subsequent to the procedure, must be recorded in the eCRF.

Refer to Section 10.1 for the known risks associated with the study device(s).

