3.1.3 Statistical Methods

Eligibility of Subjects, Exclusions, and Missing Data

The distribution of prognostic factors between patients with and without data will be examined. Statistical models that account for censored data will be employed in appropriate circumstances, e.g. for time-to-event outcomes.

For calculating the rate of stricture resolution at 24 months after initial stent placement, patients with insufficient follow-up will be excluded from the calculation; that is, only patients that have at least follow-up through 24 month visit will be included. Sensitivity analyses, such as a tipping point analysis will be performed to assess the impact of the missing data, if the data support such analysis.

When calculating rates of adverse events, missing and partial dates will be handled as follows:

Partial Date Description	Action Taken	
Entire onset date is missing	The procedure date will be used for the	
	onset date.	
The month and the day of the month are	January 1 will be used for the month and	
missing but the year is available	day of the onset date. However, if the	
	imputed date falls before the procedure	
	date, then the procedure date will be used	
	for the onset date.	
Day is missing, but the month and year are	The 1 st will be used as the day of the onset	
available	date. However, if the imputed date falls	
	before the procedure date, then the	
	procedure date will be used for the onset	
	date.	

Baseline Comparability

Baseline data will be analyzed to assess the comparability of the treatment groups. Patient demographics, clinical history, risk factors, and procedure characteristics will be summarized using descriptive statistics (mean, standard deviation, n, minimum, maximum) for continuous variables and frequency statistics for discrete variables. Statistical testing will be performed using appropriate methods.

Post-Procedure Endpoints

The treatment effect due to important prognostic factors at the baseline level for both groups will be assessed using the logistic regression model for categorical outcomes, analysis of covariance model for continuous outcomes, or stratified methods, as appropriate.

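### A never-re-stented subject who dies of a stent or procedure complication before month 24 is dropped from the primary rate instead of counted as unresolved; the resulting bias follows whichever arm has more such deaths.

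*SAP*

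**What the plan says.** **Failure.** SAP 7.3 (Rules and Definitions) and Protocol 4.1.2 share the same two-part list. The first part is "Primary endpoint failures are 1) subjects who are re-stented during follow-up after the per-protocol stenting period". The second is "2) subjects who have not been re-stented at month 24 but have alkaline phosphatase level exceeding 2 times the level" at completion of stenting. Neither part names death, and the second needs a month 24 laboratory value.

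**Success.** Success also needs that visit: "Absence of cholestasis at the 24 month visit, defined as alkaline phosphatase level not exceeding 2 times the level" at completion of stenting.

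**Who is counted.** SAP 3.1.3 says that "patients with insufficient follow-up will be excluded from the calculation" and that "only patients that have at least follow-up through 24 month visit will be included". It makes no exception for death. Protocol 8.3 leaves missing data to the SAP.

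**Sensitivity.** The same SAP section adds: "Sensitivity analyses, such as a tipping point analysis will be performed to assess the impact of the missing data, if the data support" such an analysis. It does not say how a death would be coded.

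**Death as a risk and as a record.** Protocol 10.1 lists death, apart from death through ordinary progression of disease, among the potential complications of metal stent placement and again of stent removal. Protocol 11.1 says where it is recorded: "Death should not be recorded as an AE, but should only be reflected as an outcome of a specific SAE".

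**The concern.** Read together, these rules place a subject who dies before month 24 without late re-stenting in no category. Such a subject cannot be a success, is not on the failure list, and is removed from the denominator. For a death unconnected with treatment that may be acceptable. For a fatal stent or procedure complication it means that the worst result of treatment weighs less in the primary comparison than a repeat stent does.

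The exclusion then depends on outcome. If fatal complications are unevenly spread, the arm with more of them loses failures from its denominator and its resolution rate looks better than it was. In a non-inferiority trial that can move the conclusion either way, depending on the arm.

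The two SAP sections also disagree about one kind of subject. Someone re-stented after the stenting period who then dies or is lost before month 24 is a failure under SAP 7.3 and excluded under SAP 3.1.3.

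**Working it through.** **Inputs from the documents** (SAP 3.1.2, Protocol 8.1): Farrington-Manning test, one-sided 0.05; 66% resolution expected in both arms; margin 20 points; 74 per arm evaluable, 82 per arm enrolled. The printed hypotheses have the inequality the wrong way round for a resolution rate. I use the evident intent, H0: metal − plastic ≤ −0.20.

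**Assumed:** the death rates, because the documents give none.

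**1. The plan's own figure.** Unpooled, n = 2 × 0.66 × 0.34 × (1.645 + 0.842)² / 0.20² = 69.4, so 70 per arm. The Farrington-Manning version gives 69. The stated 74 is not reproduced but errs on the safe side (power at 74 about 83%). This has no bearing on the handling of death.

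**2. One trial, two codings.** The statistic is

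z = (p̂M − p̂P + 0.20) / √[ p̃M(1 − p̃M)/nM + p̃P(1 − p̃P)/nP ],

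where the p̃ are the maximum-likelihood rates constrained to differ by −0.20. Take 82 per arm, plastic 54/82 (65.85%), and metal with 47 resolved and 2 fatal complications.

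- Deaths dropped, 47/80: p̃ = 0.5157 and 0.7157; z = (0.5875 − 0.6585 + 0.20) / 0.0749 = 1.72; p = 0.0425, non-inferior.
- Deaths counted as failures, 47/82: p̃ = 0.5103 and 0.7103; z = (0.5732 − 0.6585 + 0.20) / 0.0745 = 1.54; p = 0.062, not shown.

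Neighbouring counts show how narrow this is. With deaths counted, 48/82 passes anyway (p = 0.044). With one death dropped, 47/81 fails (p = 0.052). With two dropped, 46/80 fails (p = 0.060). With four dropped, 46/78 passes (p = 0.041), against p = 0.085 for 46/82.

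**3. Chance of a false pass.** Set the true rates, with deaths counted as failures, at 46% metal and 66% plastic, exactly on the margin. If a fraction d of an arm dies and is dropped, the rate among those remaining is 0.46/(1 − d) or 0.66/(1 − d). The probability of passing was summed exactly over the binomial numbers of deaths and resolutions, 82 randomized per arm.

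| Deaths, metal | Deaths, plastic | Apparent deficit (points) | Chance of passing |
|---|---|---|---|
| 0 | 0 | 20.0 | 5.7% |
| 2% | 0 | 66.0 − 46.9 = 19.1 | 6.7% |
| 3% | 0 | 66.0 − 47.4 = 18.6 | 7.5% |
| 5% | 0 | 66.0 − 48.4 = 17.6 | 9.4% |
| 3% | 2% | 67.3 − 47.4 = 19.9 | 5.2% |
| 5% | 5% | 69.5 − 48.4 = 21.1 | 3.9% |
| 0 | 5% | 69.5 − 46.0 = 23.5 | 1.8% |

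The first row exceeds 5% because the test is approximate at this sample size, so 5.7% is the fair reference for the others.

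**4. A different target.** If 46% and 66% are instead the rates among survivors, 5% metal-only deaths give a 5.2% chance of passing.

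**The case against.** A reader might infer that the rule favours metal, or that the test no longer holds its 5% level. The documents support neither. The exclusion is identical in both arms, no death rate is given, and nothing suggests that fatal complications will be commoner with metal. Plastic subjects have additional planned exchange procedures at months 4 and 8. A one-point metal excess (3% against 2%) leaves the false-pass chance at about 5.2%. The loss of level also depends on defining the rate with deaths as failures; defined among survivors, the level holds. What stands is that the plan never says which of these rates it means to estimate, while its completer rule in effect chooses the second.

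Nor is it fair to say that the plan ignores such deaths. It compares prognostic factors between subjects with and without data, foresees sensitivity analyses such as tipping point, and tests adverse events between arms with two-sided exact tests. These would bring a fatal imbalance to light. They do not change the primary conclusion, and the tipping-point analysis is conditional with no coding for death. Analysing the ITT cohort (SAP 4.1) does not help either, because the follow-up restriction applies to the rate itself.

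It is also true that the worked trial sits on a knife edge, and that this is one instance of a completer rule that removes every early loss. The instance deserves its own sentence because, unlike an ordinary dropout, a fatal treatment complication has a known outcome.

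**Conclusion.** The gap is real and follows directly from the text: a fatal stent or procedure complication in a never-re-stented subject is discarded from the primary rate. Its effect has no fixed direction. Measured against counting such deaths as failures, assumed metal-only deaths of 2% to 5% raise the chance of a false pass from 5.7% to between 6.7% and 9.4%. Equal or plastic-heavy deaths make passing harder (3.9% and 1.8% in the 5% cases). If such deaths are rare or nearly balanced, little changes.

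These figures rest on assumed death rates, 82 per arm, and true rates of 46% and 66%. The point should be settled before outcomes are known: the study is non-blinded, and a handful of deaths could decide a borderline result.

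**What to change.** 1. In Protocol 4.1.2 and SAP 7.3, add a third failure type: death before the month 24 visit that is the outcome of an SAE recorded as related to the stent or to a stent procedure, counted whatever the length of follow-up.
2. In SAP 3.1.3, state that a subject re-stented after the per-protocol stenting period stays in the rate as a failure even if the subject then dies or is lost. This reconciles SAP 3.1.3 with SAP 7.3.
3. Pre-specify, without condition, a sensitivity analysis that counts every death before month 24 as a failure in both arms, so that the conclusion does not rest on unblinded attribution of cause.

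**Cost.** Two or three sentences and one table. SAEs are already reported (Protocol 11.3.1), and investigators already assess relationship to device and procedure (Protocol 11.2 and 15.2). There is no category for biliary disease as a cause, so the failure type should keep to stent and procedure relatedness. Protocol 11.2 speaks of the investigational product; it should be made clear that plastic stents are assessed in the same way.

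**Downsides.** Resolution rates may fall slightly. There is room for that: at 62% in both arms the Farrington-Manning requirement is 72 per arm, still below 74. The main analysis would also take in the investigator's unblinded judgement of relatedness, which is why item 3 is needed.
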